### 3 OBJECTIVES AND ENDPOINTS

OBJECTIVES	ENDPOINTS	JUSTIFICATION FOR ENDPOINTS
Primary		
To assess the efficacy of immersive Skills-Based VR and Distraction VR in improving perceived pain from baseline to Day 30. The trial will be considered a success if there is statistical evidence of improvement in either VR group compared to sham VR.	The change from study baseline to Day 30 in pain interference as measured by the 8-item PROMIS Pain Interference scale is the primary endpoint. This scale measures the consequences of pain on relevant aspects of life, including the extent to which pain hinders engagement with social, cognitive, emotional, physical, and recreational activities.  The study will be considered a success if there is a statistically significant difference of 5 points in the Pain Interference score between participants in either the Skills-Based or Distraction VR arm compared with the Sham VR arm.	The NIH Pain Consortium Research Task Force (RTF) draft standards for research on cLBP recommend a uniform minimal data set that includes self-reported measures of pain interference.   The PROMIS PI scale is a validated instrument with excellent content validity, construct validity, and reliability in patients with chronic pain. Past work indicates that changes of 3.5 to 5.5 points in PROMIS-PI scores of people with LBP can be considered meaningful. 
Secondary		

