### 9 STATISTICAL CONSIDERATIONS

#### 9.1 STATISTICAL HYPOTHESES

- **Primary Efficacy Endpoint(s):**

Primary Outcome: Pain interference over time as measured by PROMIS-Pain Interference 8a (T-Scored, Continuous).

Hypothesis: Immersive VR (Skills-based VR or Distraction VR) will lead to a greater improvement in pain interference than Sham VR over 30-day period.

Comparisons: Superiority for both of the following (1) Distraction VR therapy vs. sham VR therapy; (2) skills-based VR therapy vs. sham VR therapy.

Additional comparison: If there is a statistically significant difference in Skills based VR vs Sham VR, then a third test will be completed (3) Skills-based VR therapy vs Distraction VR therapy.

- **Secondary Efficacy Endpoint(s):**

Secondary Outcome: Pain interference over time as measured by PROMIS-Pain Interference 8a (T-Scored, Continuous).

Hypothesis: Immersive VR (Skills-based VR or Distraction VR) will lead to a greater improvement in pain interference than Sham VR at Day 60 and Day 90.

Comparisons: Superiority for both of the following (1) Distraction VR therapy vs. sham VR therapy; (2) skills-based VR therapy vs. sham VR therapy.

Additional comparison: If there is a statistically significant difference in Skills based VR vs Sham VR then a third test will be completed (3) Skills-based VR therapy vs Distraction VR therapy.

Secondary Outcome: Pain catastrophizing over time as measured by Pain Catastrophizing scale (PCS) short form.

Hypothesis: Skills-based VR will lead to a greater improvement in Pain catastrophizing than distraction-based VR or Sham VR.

Comparisons: Superiority for both of the following (1) Distraction VR therapy vs. sham VR therapy; (2) skills-based VR therapy vs. sham VR therapy, if there is a statistically significant difference in Skills based VR vs Sham VR then a third test will be completed (3) Skills-based VR therapy vs Distraction VR therapy

Secondary Outcome: Anxiety over time as measured by PROMIS Anxiety.

Hypothesis: Skills-based VR will lead to a greater improvement in PROMIS Anxiety than distraction based VR or Sham VR.

Comparisons: Superiority for both of the following (1) Distraction VR therapy vs. sham VR therapy; (2) skills-based VR therapy vs. sham VR therapy, if there is a statistically significant difference in Skills based VR vs Sham VR then a third test will be completed (3) Skills-based VR therapy vs Distraction VR therapy

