## 9.2 SAMPLE SIZE DETERMINATION

### Sample Size calculations

The primary goal of this aim is to test the efficacy of immersive VR in improving perceived pain. The trial will be a success if there is statistical evidence that either immersive VR group is better than control or sham VR. Preliminary studies showed that the PROMIS pain interference scale has a SD of 10. Assuming that the SD at baseline ( $SD_0$ ) and at 30 days ( $SD_1$ ) are similar and equal to 10 for this population, the variance for the difference in PROMIS from baseline to 30 days after intervention is  $Var_{diff} = SD_0^2 + SD_1^2 - 2\rho SD_0 SD_1$ , where  $\rho$  is the correlation coefficient between measurements at baseline and 30 days. A conservative estimate of this variance is achieved when  $\rho = 0$ . Therefore, the estimate  $SD_{diff} = (10^2 + 10^2)^{0.5} = 14.14$ . Let  $m_c$ ,  $mv_1$ , and  $mv_2$  be the mean change in PROMIS score from baseline to 30 days for the control, VR1, and VR2 groups, respectively.

We estimate power by simulating 10000 trial replicates and testing the null hypothesis that  $H_0: m_c = mv_1 = mv_2$  versus the alternative hypothesis that  $H_1: m_c \neq mv_1$  or  $m_c \neq mv_2$ . To maintain the familywise error rate at 0.05, a two-sample t-test is used to compare the control arm to each VR arm and the test is declared statistically significant if the p-value of the two-sided test is less than 0.025. Under the alternative hypothesis that  $|m_c - mv_1| = |m_c - mv_2| = 5$ , data from 120 patients in each of the three arms achieve 83% power to detect a clinically meaningful effect 5 units in the PROMIS score. The actual type I error rate is 0.049. For the secondary outcome of comparison between the two VR arms, we test the null hypothesis that  $H_0: mv_1 = mv_2$  versus the alternative hypothesis that  $H_1: mv_1 \neq mv_2$  at the two-sided 0.05 level of significance if there is statistical evidence that both VR arms are better than control. Using the same assumptions as above and simulating 10000 trial replicates, then if both VR arms are better than the control arm, we can achieve 71.4% power to detect 5 units in PROMIS score between the two VR arms. This power was derived under the alternative hypothesis  $|m_c - mv_1| = 5$  and  $|mv_1 - mv_2| = 5$ . The actual type I error rate for this conditional test is 0.02.

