#### 9.4.2 ANALYSIS OF THE PRIMARY EFFICACY ENDPOINT(S)

The goal of this analysis is to test the effectiveness of immersive VR in improving measures of pain interference. The trial will be a success if there is statistical evidence that either immersive VR group is better than sham VR.

The primary efficacy endpoint is the change from study baseline to Day 30 in pain interference as measured by PROMIS-PI t-score. The primary analysis will compare each treatment group separately to the control group using a linear mixed model repeated measures (MMRM) analysis. The repeated measures are the change from baseline PROMIS-PI t-score obtained at Days 7, 15, and 21, respectively. The model will include fixed categorical effects for treatment, week, treatment by week interaction, and the baseline PROMIS-PI t-score as a continuous covariate. We will employ the Stata *xtmixed* command

with restricted maximum likelihood estimation (REML) and an unstructured within-patient covariance structure for this model. We will evaluate the assumptions of the model, including normality, using residual and other diagnostic plots of model fit.

From this model, we will estimate least squares means, standard errors, treatment differences in least squares means, and 95% confidence intervals for each time period. Primary inference will be based on the treatment comparison of least squares means for Day 30, and a p-value will be presented for this time period only. The null hypothesis is that the mean difference in the primary endpoint between the treatment groups and the sham control group is zero, versus the alternative hypothesis that these differences are not zero. The hypotheses can be expressed as follows:

$$H0_a: \mu_{SB} - \mu_{control} = 0 \text{ versus } H1_a: \mu_{SB} - \mu_{control} \neq 0$$

$$H0_b: \mu_D - \mu_{control} = 0 \text{ versus } H1_b: \mu_D - \mu_{control} \neq 0$$

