### 3.5 Determination of Sample Size

The primary aim is to test the efficacy of immersive VR in improving perceived pain. The trial will be a success if there is statistical evidence that either immersive VR group is better than control (sham) VR.

Preliminary studies showed that the PROMIS pain interference scale has a SD of 10. Assuming that the SD at baseline (SD0) and at 30 days (SD1) are similar and equal to 10 for this population, the variance for the difference in PROMIS from baseline to 30 days after intervention is  $\text{Var}_{\text{diff}} = \text{SD0}^2 + \text{SD1}^2 - 2 \rho \text{SD0} \text{SD1}$ , where  $\rho$  is the correlation coefficient between measurements at baseline and 30 days. A conservative estimate of this variance is achieved when  $\rho = 0$ . Therefore, the estimate  $\text{SD}_{\text{diff}} = (10^2 + 10^2)^{0.5} = 14.14$ . Let  $mc$ ,  $mv1$ , and  $mv2$  be the mean change in PROMIS score from baseline to 30 days for the control, VR1, and VR2 groups, respectively. We estimate power by simulating 10000 trial replicates and testing the null hypothesis that  $H_0: mc = mv1 = mv2$  versus the alternative hypothesis that  $H_1: mc \neq mv1$  or  $mc \neq mv2$ . To maintain the familywise error rate at 0.05, a two-sample t-test is used to compare the control arm to each VR arm and the test is declared statistically significant if the p-value of the two-sided test is less than 0.025. Under the alternative hypothesis that  $|mc - mv1| = |mc - mv2| = 5$ , data from 120 patients in each of the three arms achieve 83% power to detect a clinically meaningful effect 5 units in the PROMIS score. The actual type I error rate is 0.049. For the secondary outcome of comparison between the two VR arms, we test the null hypothesis that  $H_0: mv1 = mv2$  versus the alternative hypothesis that  $H_1: mv1 \neq mv2$  at the two-sided 0.05 level of significance if there is statistical evidence that both VR arms are better than control. Using the same assumptions as above and simulating 10000 trial replicates, then if both VR arms are better than the control arm, we can achieve 71.4% power to detect 5 units in PROMIS score between the two VR arms. This power was derived under the alternative hypothesis  $|mc - mv1| = 5$  and  $|mv1 - mv2| = 5$ . The actual type I error rate for this conditional test is 0.02.

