#### 3.5.1 Power Estimation

For the primary endpoint of the study, there is 83% power to detect a clinically meaningful effect size of 5 units in PROMIS score between control and either VR arms at the 0.05 level of significance. This requires 360 patients randomized on a 1:1:1 ratio.

For one of the secondary endpoints of comparison between the two VR arms, we test the null hypothesis that  $H_0: mv1 = mv2$  versus the alternative hypothesis that  $H_1: mv1 \neq mv2$  at the two-sided 0.05 level of significance if there is statistical evidence that both VR arms are better than control. Using the same assumptions as above and simulating 10000 trial replicates, then if both VR arms are better than the control arm, we can achieve 71.4% power to detect 5 units in PROMIS score between the two VR arms. This power was derived under the alternative hypothesis  $|mc - mv1| = 5$  and  $|mv1 - mv2| = 5$ . The actual type I error rate for this conditional test is 0.02.

For assessing the effect of VR on treatment response, we estimate power using a logistic regression model, accounting for all possible confounding factors as described in the protocol.

The outcome variable is treatment response (binary) and the predictor of interest is VR type, Distraction versus Skills-based. Table 1 gives the minimum odds ratio that can be detected with 80% power with the two-sided 0.05 level of significance as a function of baseline probability of positive response when a patient is treated with traditional VR and  $R^2$ , the proportion of variability in the predictor of interest (VR type) that is explained by all relevant baseline covariates in the model using data from 120 patients in the Distraction VR arm and 120 in the Skill-based VR arm. For example, data from 240 patients achieve 80% power to detect an odds ratio of 2.19 if the probability of positive response when a patient is treated with Distraction VR is 0.3 and 10% of the variability in VR type is explained by all other baseline covariates in the model. These odds ratios vary between 2.01 and 2.8 and are clinically meaningful. Therefore, we have enough power to test statistical significance of predictors of interest in the multivariable logistic regression model.

**Table 1.** Minimum detectable odds ratio as a function of the proportion of variability in VR type variable that is explained by all other relevant covariates in the model and the baseline probability of positive treatment response.

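### Primary success is worded two ways, any significant difference from sham or a significant difference of 5 points, and the plan should say that the first one governs

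*Protocol*

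**What the plan says.** The primary row of the objectives table holds two success sentences. The objective column reads "The trial will be considered a success if there is statistical evidence of improvement in either VR group compared to sham VR". The endpoint column reads "The study will be considered a success if there is a statistically significant difference of 5 points in the Pain Interference score", for either VR arm against sham. The SAP repeats both in 3.2 (Study Objectives and Endpoints).

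Elsewhere no size is required:

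- Protocol 9.1: immersive VR "will lead to a greater improvement in pain interference than Sham VR over 30-day period".
- Protocol 9.4.2, and SAP 4.6.1 in the same terms: "The null hypothesis is that the mean difference in the primary endpoint between the treatment groups and the sham control group is zero". Both sections also open with their own success sentence, which asks only that either immersive arm be better than sham.
- Protocol 9.2 and SAP 3.5: each VR arm is compared with control, and "the test is declared statistically significant if the p-value of the two-sided test is less than 0.025". Here 5 points is the effect to be detected: the design is said to "achieve 83% power to detect a clinically meaningful effect 5 units in the PROMIS score". SAP 3.5.1 repeats that "there is 83% power to detect a clinically meaningful effect size of 5 units in PROMIS score between control and either VR arms".

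Two nearby statements bear on how the rule would operate. Protocol 9.4.2 and SAP 4.6.1 give the primary test a two-sided 5% level without adjustment, whereas the sizing uses 0.025 per comparison. SAP 6.3 promises familywise control at 0.05 by gatekeeping and a closed procedure but does not name the procedure. Protocol 9.4.2 also says "The repeated measures are the change from baseline PROMIS-PI t-score obtained at Days 7, 15, and 21, respectively", which leaves out Day 30, the time point of primary inference. SAP 4.6.1 includes Day 30.

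**The concern.** A success criterion should give one answer for any result. Here the same table row gives two. The zero rule is met by any significant difference favouring VR. The 5-point sentence can fairly be taken as a relevance bar on top of significance: the sizing text calls 5 units clinically meaningful, and the justification column of the same row calls changes of 3.5 to 5.5 points meaningful. A test against zero does not exclude such a bar, because a trial can test against zero and also require the estimate to reach a stated size.

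At stake is how a moderate positive result is declared. A significant Day 30 difference a little below 5 points is a success by one sentence and a failure by the other, and the plan does not say which sentence decides. The power statement supports only one of the two.

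**Working it through.** **Inputs (Protocol 9.2, SAP 3.5).** SD of a single score 10 at both times; correlation 0, so SD of change = √(10² + 10²) = 14.14; 120 per arm; two-sided 0.025 per comparison; true difference 5 in both VR arms. The two comparisons share the sham arm, so with equal arms their estimates have correlation 0.5.

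**Step 1: reproduce the 83%.**

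- SE of a difference = 14.14 × √(2/120) = 1.826.
- Critical value t(0.9875; 238 df) = 2.256.
- Smallest significant difference = 2.256 × 1.826 = 4.12 points.
- Probability that at least one estimate reaches 4.12 (bivariate normal, correlation 0.5, both means 5) = 0.832. Simulated t-tests also give 0.832. The plan states 83%.
- One comparison alone has power of about 0.69. So the 83% is either-arm power, tested against zero.

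**Step 2: the disputed zone.** If the observed difference must also reach 5, the threshold moves from 4.12 to 5. Estimates from about 4.1 up to 5 points are then classified differently by the two sentences. Example: an observed 4.5 gives t = 4.5/1.826 = 2.46, p = 0.014. That is below 0.025 but short of 5.

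**Step 3: true difference needed to keep 83%.** Solve P(at least one estimate ≥ 5) = 0.83 with SE 1.826 and correlation 0.5. The solution is a true difference of 5.87 points in both arms, against the planned 5.

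**Step 4: a smaller true effect.** With a true difference of 3.5 points in both arms, the low end of the range that the table calls meaningful, simulated either-arm success is 52.6% under the zero rule and 32.0% if 5 must also be observed.

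**Step 5: sensitivity to the SD.** The planned MMRM adjusts for baseline. With the plan's correlation of 0, the adjusted SD is 10 × √(1 − 0²) = 10. Then SE = 10 × √(2/120) = 1.291 and the threshold is 2.256 × 1.291 = 2.91. The disputed zone widens to about 2.9 to 5 points, and the true difference needed for 83% is 5.61.

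**Step 6: the significance level.** Two tests at an unadjusted 5% each give a simulated familywise error of 0.090 and a threshold of about 3.6 points. At 0.025 each, the simulated familywise error is 0.046; the plan's own simulation of 10,000 replicates gives 0.049.

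**The case against.** The best reply is that the operative text already settles the matter. Protocol 9.4.2 and SAP 4.6.1 write out the null as zero and carry their own success sentence. The hypotheses agree, and wherever 5 is used in a calculation it is the effect to detect. SAP 3.5.1 comes close to paraphrasing the disputed sentence as a power statement. On this view the fault is one loose sentence copied into two tables. The Day 30 estimate and its 95% confidence interval will be reported anyway, so any reader can see whether 5 was reached.

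Much of this stands. The hypothesis test is not ambiguous, and the documents lean clearly towards the zero rule. What remains is that they do so only by implication, while the 5-point sentence is itself worded as a criterion for success in both documents.

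Three stronger readings are tempting, and the documents do not support them:

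- **That 5 is the null value.** This contradicts the null written in Protocol 9.4.2 and SAP 4.6.1, and no section mentions a margin.
- **That power falls to 67% if 5 must be observed.** With the true difference set exactly at the threshold and correlation 0.5, the chance that at least one estimate reaches its own mean is 1 − (1/4 + 1/12) = 2/3, whatever the SD or sample size. The figure follows from that choice and says little about this trial.
- **That the rule could be picked after seeing the data.** Protocol 8.1 planned randomization to end on 9/5/2023, and the current revision, dated 19 October 2023, still carries both sentences. But the SAP version dated 09/14/21 already has the zero null, statisticians work with blinded A, B and C labels, and no interim comparison is planned. A dated blinding note is good practice; the documents give no ground for suspicion.

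**Conclusion.** The concern holds as a wording conflict in the primary success criterion that should be fixed. The zero rule is the better-supported reading, but nothing states that it governs. The only serious rival is that the observed difference must also reach 5 points.

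Under that rival reading and the plan's own inputs, estimates of about 4.1 to 5 points (about 2.9 to 5 if the baseline-adjusted SD is 10) would be declared differently by the two sentences. Keeping 83% either-arm power would need a true difference of about 5.9 points in both arms. If 5 is only the planning difference, no result is in dispute. The stated 83% is correct for the zero rule and for no other.

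These figures assume a t-test on change scores, 120 analysed per arm, equal effects in both VR arms and 0.025 per comparison. Neither the planned test nor the sample size needs to change under the zero rule.

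**What to change.** In Protocol Section 3 and SAP 3.2 (Study Objectives and Endpoints), replace the 5-point sentence with one rule, for example: *Success is a significant Day 30 MMRM difference from zero favouring VR in either arm, with familywise error held at 0.05 (SAP 6.3); 5 points is the planning difference, reported beside the estimate and its 95% confidence interval.* Record the date of the change and the blinding status at that date. If the sponsor does mean that the observed difference must reach 5, say so and restate the power.

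Two further edits are needed for the rule to work:

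- In Protocol 9.4.2 and SAP 4.6.1, replace the unqualified 5% level with the 0.025 per comparison used in the sizing, or with the closed procedure of SAP 6.3 once it is named. Under Bonferroni or Holm, either-arm success needs one p-value of 0.025 or less.
- In Protocol 9.4.2, list Day 30 among the repeated measures, as SAP 4.6.1 does.

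Cost: wording in both documents and a dated note. The sponsor gives up 5 points as a condition for success. No new data or patients are needed.

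A separate and lesser item, to be reconciled on its own: PCS-SF6 is described as a rate of scores of 7 or more (Protocol Section 3 and 8.1, SAP 3.2) but analysed as a continuous score (Protocol 9.4.3, SAP 4.6.2). It adds nothing to the weight of this point.
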